### Analysis of Secondary Endpoints:

Secondary endpoints in this study include patient satisfaction (assessed by subjects' responses to questions 1, 7 and 8 of the DTSQc), quality of life score, insulin dose, rate of hypoglycemia, number of episodes of severe hyperglycemia and hypoglycemia. For a continuous secondary outcome (e.g. quality of life score), our analysis will be focused on determining whether the outcome difference between period after crossover (i.e. period 2) versus the period before crossover (i.e. period 1) in the Insulclock group is similar to that in the conventional device group. We will perform the analysis based on paired t-tests. Linear mixed models will be conducted to assess the study group difference while accounting for potential confounders. Appropriate transformations may be applied to determine the final linear models. For binary secondary outcomes, we will follow the analysis plan proposed for the primary endpoint.

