# **Study Aims:**

Aim 1. To determine whether the Insulclock system results in improved treatment adherence and reductions in treatment irregularities (insulin omission, mistiming and dosing) compared to conventional insulin pen device. Patients with inadequately controlled T2D treated with oral antidiabetic agents and basal insulin (NPH, glargine or detemir) will be randomized to Group A: Insulclock device with feedback or to Group B: Insulclock without feedback. All patients will use the Insulclock device attached to glargine U100 insulin pens (SoloStar®) during the study period. Participants in Group A will receive daily information on their smartphone on insulin administration (time and dosing) as well as reminders in the event of missing doses. Participants in Group B, will use the Insulclock, but will not receive feedback on insulin administration. Differences in insulin injection irregularities (omission, mistiming and dosing) will be compared at each clinic visit during the study period.

**Hypothesis:** The Insulclock device will improve adherence reducing insulin omission, mistiming and dosing errors compared to standard pen device.

Aim 2. To determine whether the Insulclock system yields higher treatment satisfaction scores in poorly controlled patients with T2D compared to a conventional insulin pen device. Patients with inadequately controlled T2D (HbA1c  $\geq$  7.0%) treated with oral antidiabetic agents and basal insulin once daily (NPH, glargine or detemir) will be enrolled in a 24 week randomized, cross-over clinical trial comparing the

use of Insulclock device system vs standard insulin pen. Treatment satisfaction will be assessed with the Diabetes Treatment Satisfaction Questionnaire Status (DTSQs) to be administered at baseline (week 0) and at weeks 12 and 24 to assess relative changes in the DTSQ between interventions. The amplitude of the score on the DTSQc gives the degree of change in satisfaction while the direction (positive or negative) will provide guidance on the preference of therapy.

**Hypothesis:** The Insulclock device will improve treatment satisfaction compared to standard insulin pen device.

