# **Assessment of Results:**

The primary outcome of *treatment adherence* with the use of Insulclock with feedback or no feedback information (blinded) will be determined by the percentage of patients and number of insulin omission, mistiming and dosing. Number insulin irregularities will be registered on the Insulclock device and data will be retrieved during each clinic visit.

**For treatment satisfaction**, subjects' responses to questions 1, 7 and 8 of the DTSQc will be used. A comparison of the score on the DTSQs from week 12 to week 24 as well as using the score on the other questions of the DTSQc, which would overcome the ceiling limitation of using the DTSQs by itself, will also be used to assess treatment satisfaction . The Diabetes Treatment Satisfaction Questionnaire Status (DTSQs) form will be administered at weeks 0, 12 and 24.

Questionnaires will be given at week 0 for standardization purposes. The amplitude of the score on the DTSQc gives the degree of change in satisfaction while the direction (positive or negative) will provide guidance on the preference of one device over the other (i.e., if we predict that patients greatly prefer alarm reminders over nothing and he/she started the group 1 with daily reminders then transitioned to group 2 without the daily reminders, his/her score would be '-3', whereas if he/she was initially not getting the daily reminders followed by the daily reminders then the score would be '+3').

**Ouality of life** will be assessed at baseline and again at weeks 12 and 24 in order to determine the impact of the type of therapy on this outcome. Patients will be given the Diabetes Quality of Life Clinical Trial Questionnaire-Revised (DQLCTQ-R), the Problem Areas In Diabetes scale (PAID) and the Elderly Diabetes Burden Scale (EDBS) at baseline, weeks 12 and 24 to assess their quality of life and any potential impact of the treatment regimen .

*Glycemic Control* will be assessed via HbA1c at weeks -1, 12 and 24 and via fasting blood glucose averages at weeks 0, 12 and 24 from point of care testing during the preceding week.

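### The satisfaction endpoint is defined on the DTSQc, but only the DTSQs is given a time point, and the paired t-test named for it does not match the between-group contrast described

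*Combined protocol and SAP*

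**What the plan says.** **Which instrument.** Analysis of Secondary Endpoints lists satisfaction as "responses to questions 1, 7 and 8 of the DTSQc), quality of life score". Assessment of Results uses the same three DTSQc questions. It adds a DTSQs comparison between weeks 12 and 24 and the remaining DTSQc questions, "which would overcome the ceiling limitation of using the DTSQs by itself". Secondary Objectives lists satisfaction by the DTSQs. Aim 2 under Study Aims begins "Treatment satisfaction will be assessed with the Diabetes Treatment Satisfaction Questionnaire Status (DTSQs" and then interprets the other form: "The amplitude of the score on the DTSQc gives the degree of change in satisfaction".

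**When.** Assessment of Results states "The Diabetes Treatment Satisfaction Questionnaire Status (DTSQs) form will be administered at weeks 0, 12 and 24". Aim 2 and the text after the titration table give the DTSQs the same weeks. The DTSQs also appears in the lists for Visit 2 preparation, the crossover visit and Visit 14. The DTSQc has no week or visit anywhere. The nearest sentence, "Questionnaires will be given at week 0 for standardization purposes", names no form.

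**How analysed.** For continuous secondary outcomes, Analysis of Secondary Endpoints asks whether the period 2 versus period 1 difference in the Insulclock group "is similar to that in the conventional device group". It continues "We will perform the analysis based on paired t-tests" and then adds linear mixed models for the study group difference.

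**Sign.** The example in Assessment of Results scores the same liking for reminders as -3 in a patient who had them first and +3 in a patient who had them second.

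**The concern.** Two things do not fit together. First, the form that defines the endpoint is not the form that is scheduled. A site working only from the written schedule would hold DTSQs scores and no DTSQc scores, and a retrospective change rating that was not taken at the time cannot be recovered later.

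Second, the contrast described is between groups, while the test named is within patients. The gap is widest for the DTSQc, which gives one signed change per patient and so has no second value to pair with. Its sign also depends on the order of treatment, so the analysis has to say how the two sequences are compared.

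At stake is whether Aim 2 is answered with the measure the analysis section promises, and whether the analysis is fixed before the data are seen.

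**Working it through.** **1. Instrument and timing, side by side**

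| Section | Form named | Week or visit given |
|---|---|---|
| Study Aims, Aim 2 | DTSQs; DTSQc interpreted | DTSQs only: 0, 12, 24 |
| Secondary Objectives | DTSQs | none |
| Visit 2 preparation | DTSQs | that visit |
| Crossover visit | DTSQs | that visit |
| Visit 14 list and text after the titration table | DTSQs; DTSQc interpreted in the text | DTSQs only: Visit 14; 0, 12, 24 |
| Assessment of Results | DTSQc questions 1, 7, 8; DTSQs also | DTSQs only: 0, 12, 24 |
| Analysis of Secondary Endpoints | DTSQc questions 1, 7, 8 | none |

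The visit lists alone would be weak evidence, since they omit the quality-of-life forms too. But Assessment of Results times those forms explicitly (baseline, weeks 12 and 24). The DTSQc has no such sentence.

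**2. What a single signed score needs**

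Let d be the device effect and s a shift common to both sequences (a period effect). The mean DTSQc score is s + d when reminders come second and s - d when they come first.

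- Between sequences: (s + d) - (s - d) = 2d. Half the difference is d, free of s. With the example's illustrative scores, (3 - (-3))/2 = 3.
- One-sample (paired-type) test after reversing the sign in the reminders-first sequence: the means become d + s and d - s. With n1 and n2 completers the overall mean is d + s(n1 - n2)/(n1 + n2). This equals d if s = 0. If s is not 0, it equals d only with equal sequences, and even then the aligned scores carry extra variance s².

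So the paired-type test needs a sign reversal and rests on there being no period effect. The plan writes down neither for this endpoint.

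**3. The plan's power figure, reproduced**

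Inputs from Power Considerations: 40 per group, 15% attrition, difference 0.41 SD, within-subject correlation 0.3, alpha 0.05 (sidedness not stated; two-sided reproduces the figure).

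- Completers: 80 × 0.85 = 68, or 34 per sequence.
- SD of a within-patient difference: √(2 × (1 - 0.3)) = 1.183 SD.
- Paired t-test: noncentrality 0.41/1.183 × √68 = 2.857, df 67, power 80.4%. This agrees with the stated figure of over 80%.

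**4. The matching test on the scheduled DTSQs**

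The period 2 minus period 1 differences average +0.41 and -0.41 SD in the two sequences, a gap of 0.82 SD.

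- 34 per sequence: 0.82/(1.183 × √(2/34)) = 2.857, df 66, power 80.4%.
- 32 per sequence, the arm size under Number of subjects planned: 0.82/(1.183 × √(2/32)) = 2.77, df 62, power 77.9%. The paired test with 64 patients also gives 77.9%.

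Changing the test therefore costs essentially no power. The drop to 77.9% comes from the smaller arm size.

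**5. DTSQc power**

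The documents give no DTSQc SD and set no target difference for it, so no power figure applies.

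**The case against.** The strongest reply is that the intent is recoverable. The signed example describes a patient who has already switched, so the DTSQc must come after crossover. Visit 14 is the only visit after the crossover visit that lists a satisfaction form. Analysis of Secondary Endpoints plans linear mixed models for the group difference; with one score per patient these reduce to an ordinary linear model, which is the between-sequence comparison needed. A sign-aligned one-sample test is also legitimate without a period effect, which Power Considerations assumes. And this is one secondary endpoint in a self-described pilot.

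Much of that stands. The time point can be guessed, and a suitable model class is named. What remains is that the visit is not written down, the objectives and the analysis section name different forms, and no sentence says how the model or the paired test applies to the DTSQc.

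Three stronger readings are not supported:

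- **Satisfaction cannot be assessed at all.** The DTSQs is scheduled, and Assessment of Results plans its week 12 to week 24 comparison.
- **The device effect would cancel.** That happens only if raw DTSQc scores are pooled across sequences. The plan does not propose this, and its between-group wording points away from it.
- **The trial is underpowered for satisfaction because of this.** The stated figure reproduces, and the matching test on the DTSQs has the same power.

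**Conclusion.** The point holds and should be fixed; it does not threaten the trial. The endpoint named in the analysis section has no stated collection time, the documents disagree on the instrument, and the named paired t-test does not match the contrast described in the same paragraph. The timing gap and the instrument conflict are matters of text and are certain. The test mismatch rests on reading the two groups in that paragraph as the two randomised sequences, which a crossover with period 2 versus period 1 differences implies.

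The reach is one secondary endpoint, the one that carries Aim 2. The primary adherence analysis and the power stated in Power Considerations are unaffected. The 80.4% assumes 80 patients, 15% attrition, equal sequences, correlation 0.3 and a two-sided test. Number of subjects planned instead gives 150 patients and 32 per arm, and those figures need reconciling in their own right.

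**What to change.** Choose one option and use the same instrument in Aim 2, Secondary Objectives, Assessment of Results and Analysis of Secondary Endpoints.

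- **(a) Keep the DTSQc.** State that it is given once, at Visit 14, in Aim 2, the Visit 14 section and Assessment of Results. In Analysis of Secondary Endpoints, compare scores between the two sequences by a two-sample t-test or linear model, with the device effect as half the difference. Cost: one short form at an existing visit and no change in sample size. Its power stays unstated unless a DTSQc SD is supplied.
- **(b) Use the DTSQs.** Name the DTSQs at the end of each period as the endpoint in Assessment of Results and Analysis of Secondary Endpoints, in line with Secondary Objectives. Compare period 2 minus period 1 differences between sequences by a two-sample t-test, or fit a mixed model with treatment and period terms. Cost: no new data and about 80.4% power at 0.41 SD with 34 per sequence (77.9% with 32), but the ceiling limitation that the plan cites is accepted.

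With either option, reconcile the visit weeks. The crossover visit is headed week 14 while its text says week 12, and the trial is 24 weeks in Aim 2 but 26 in Methods and Duration of study.

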# **Statistical Analysis:**

This pilot study will compare treatment irregularities (insulin omission, mistiming and dosing) between Insulclock versus conventional insulin injection pen device. We will also compare differences in glycemic control, as measured by change in mean HbA1c from baseline, number of hypoglycemic events, percentage of subjects maintaining therapy, 7-point SMBG profile, fasting plasma (FPG) profile, and HRQoL assessments (Patient reported outcomes) between groups.

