### Analysis of Primary Endpoint:

The primary outcome of treatment adherence with the use of Insulclock with feedback or no information (blinded) is whether a patient has a good adherent to the treatment regimen (assessed based on insulin omission, mistiming, and dosing). Given the 2 by 2 cross-over design, the superiority of the Insulclock system over the conventional insulin pen device will be determined by comparing the percent of patients showing a good treatment adherence with Insulclock but a poor treatment adherence with the conventional device to the percent of patients showing a poor treatment adherence with Insulclock but a good treatment adherence with the conventional device. We will perform this comparison based on McNemar's test assuming the period effect is negligible. We will further conduct logistic regression to accommodate potential period effect and adjust for other potential confounders. We will apply standard model selection and model checking procedures (such as the Hosmer-Lemeshow tests) to decide and evaluate the final model. A p value of <0.05 will be considered significant.

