### **Power Considerations**

This is a pilot study and we plan to recruit 40 subjects for each study group. Our power calculation is mainly based on the binary primary outcome. We assume no more than 15% attrition rate, and assume no period

effect. In the following table, we give the power for detecting the superiority of Insulclock based on Exact Test for Binomial proportion with alpha=0.05, under different projections for the proportion of subjects showing treatment preference (i.e. adherent under one treatment but not under the other), denoted by Ptp, and projections for the probability of preference to Insulclock given showing treatment preference, denoted by p.

	P tp					
Power		90%	80%	70%	60%	50%
р	0.6	31.2%	28.2%	21.5%	17.8%	13.9%
	0.7	87.9%	83.7%	74.9%	66.5%	55.4%
	0.8	>99%	>99%	>99%	97.6%	93.8%
	0.9	>99%	>99%	>99%	>99%	>99%

Regarding the secondary outcomes, the power calculations can be made conservatively based on superiority hypotheses without specifying the equivalent margins. For continuous secondary outcomes, we would have over 80% power to detect outcome difference of 0.41 times the standard deviation based on paired t tests, with alpha=0.05, assuming equal outcome standard deviations for Insulclock and the conventional device, and within subject correlation equal to 0.3.

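### Continuous secondary outcomes: the plan describes a comparison of period differences between the two sequences but names paired t-tests, and its mixed model does not name period

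*Combined protocol and SAP*

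**What the plan says.** Analysis of Secondary Endpoints sets the target for a continuous outcome. It takes the difference between the period after crossover and the period before, and asks whether that difference "in the Insulclock group is similar to that in the conventional device group. We will perform the analysis based on paired t-tests". A model follows: "Linear mixed models will be conducted to assess the study group difference while accounting for potential confounders". Period and sequence are not mentioned. The outcomes listed there include "quality of life score, insulin dose, rate of hypoglycemia", together with satisfaction from three DTSQc items. The opening of Statistical Analysis adds "differences in glycemic control, as measured by change in mean HbA1c from baseline" and fasting glucose.

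For the binary primary outcome, Analysis of Primary Endpoint is more explicit. After McNemar's test it says "We will further conduct logistic regression to accommodate potential period effect and adjust for other potential confounders". The secondary section carries that plan over to binary secondary outcomes only.

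Power Considerations bases its continuous-outcome figure on a within-patient device comparison: "based on paired t tests, with alpha=0.05, assuming equal outcome standard deviations for Insulclock and the conventional device". The same section, introducing the primary calculation, states "We assume no more than 15% attrition rate, and assume no period" effect.

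**The concern.** Every patient uses both conditions, so no patient belongs only to an Insulclock group or only to a conventional group. The two groups whose period differences are compared must therefore be the two orders of treatment. They hold different patients, and comparing one set of patients' differences with another set's calls for a two-sample test. A paired t-test compares two measurements on the same patient. An analyst following the section has to depart from either the contrast or the test.

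What is at stake is how a time trend common to both sequences is handled. A trend is plausible for insulin dose, HbA1c and fasting glucose, because the text under Visit 14 (End of Study) has glargine titrated towards a fasting glucose target at each visit. The documents show no such mechanism for quality of life. The between-sequence contrast removes a common trend and the within-patient device test does not. If the mixed model also omits period, nothing in the continuous analysis deals with it.

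**Working it through.** **Inputs.** From Power Considerations: 40 patients per group (80 in all), 15% attrition, equal SDs, within-patient correlation 0.3, effect 0.41 SD, alpha 0.05. Completers: 80 × 0.85 = 68. Sidedness is not stated; two-sided reproduces the plan's figure. Assumed here, because the documents give none: a common period trend π of 0.25, 0.5 or 1.0 SD in the direction of the device effect.

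**Step 1: reproduce the plan's figure.** SD of a within-patient difference = √(2 × (1 − 0.3)) = √1.4 = 1.183 SD. Standard error with 68 patients = 1.183/√68 = 0.1435. Noncentrality = 0.41/0.1435 = 2.857. The noncentral t with 67 degrees of freedom gives power 80.4%, so the stated figure of over 80% is correct for a paired device comparison with no trend.

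**Step 2: compare the two estimates.** Let D be period 2 minus period 1, τ the device effect, and n1 and n2 the completers who had Insulclock first and second.

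- Mean of D: π − τ (Insulclock first) and π + τ (Insulclock second).
- Half the between-sequence difference in D: τ, at any trend.
- Insulclock minus conventional within patient: mean τ − π (first) and τ + π (second). Pooled mean = τ + π(n2 − n1)/(n1 + n2).

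With n1 = n2 the two estimates are algebraically identical. The standard errors are not: the pooled within-patient differences are shifted by −π in one sequence and +π in the other, so their variance is about 1.4 + π². The standard error is inflated by √((1.4 + π²)/1.4), which is 1.02, 1.09 and 1.31 for the three trends.

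**Step 3: consequence with balanced completers (34/34, simulation).**

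| Trend (SD) | Paired device test: power at 0.41 SD | Paired device test: type I error | Two-sample test on D: power |
|---|---|---|---|
| 0 | 80.4% | 5% | 80.4% |
| 0.25 | 79.2% | 4.5% | 80.4% |
| 0.5 | 75.3% | 3.4% | 80.4% |
| 1.0 | 59.3% | 1.0% | 80.4% |

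The two-sample noncentrality is 0.82/(1.183 × √(1/34 + 1/34)) = 2.857 on 66 degrees of freedom. Its type I error is about 5% at every trend.

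**Step 4: unequal completers.** Bias of the paired estimate = π(n2 − n1)/(n1 + n2). With a 0.5 SD trend:

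| Completers (Insulclock first/second) | Bias (SD) | Paired power |
|---|---|---|
| 36/32 | 0.5 × (−4/68) = −0.029 | about 69% |
| 32/36 | +0.029 | about 81% |
| 38/30 | 0.5 × (−8/68) = −0.059 | about 61% |
| 30/38 | +0.059 | about 86% |

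If 12 of the 80 patients drop out at random, the hypergeometric probability of at least 36 Insulclock-first completers is 17.4%, and of at least 38 it is 1.26%. The opposite directions are equally likely, so the bias averages to zero. Average paired power over all splits is about 79%, 75% and 59% for the three trends, essentially the balanced values. The two-sample test has power 80.3% at 36/32 and 79.8% at 38/30, at any trend.

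**The case against.** The strongest reply is that the plan mirrors its primary analysis: a simple paired test that takes the period effect as negligible, then a model. In the primary section the word *other* before confounders implies that period counts as one, so the mixed model's confounders may be meant to include it. That is a fair reading. It leaves the section silent on the point, since it extends the explicit period adjustment to binary outcomes only.

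It is also fair that the trend is assumed, and that at 0.25 SD the balanced loss is about one point of power. The titration text holds doses constant once the fasting average is on target, which may limit drift in period 2 without excluding it.

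Three stronger readings are tempting, and the documents do not support them:

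- A reader might infer that the paired test estimates the wrong quantity. Under the likely reading it does not: with balanced completers its mean is half the between-sequence difference, and only the standard error differs.
- A reader might infer biased results or excess false positives. Random imbalance shifts the estimate either way and averages out. Systematic bias needs differential dropout, for which the documents give no figure.
- A reader might take the wording literally, as a paired test of period 2 against period 1. That would test time and not device: pooled over 34/34 with no device effect, it would reject in about 40%, 93% and nearly 100% of trials at the three trends. The power section's reference to the two devices makes this the less likely reading, so these rates should not set the severity.

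**Conclusion.** The point holds as a minor specification error in the secondary analyses of a pilot. The contrast described and the test named do not match, and period is not explicitly in the mixed model. Under the likely reading with balanced completers, the cost is lost power (from 80.4% to about 79%, 75% or 59%) and a conservative test. This rests on the plan's 68 completers, correlation 0.3 and 0.41 SD effect, and on assumed trends of 0.25, 0.5 and 1.0 SD. With no trend, the paired test is valid and nothing is lost.

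It is not a sample-size error, because the power figure reproduces. It matters mainly for insulin dose, HbA1c and fasting glucose. The DTSQc lies outside the contrast: Assessment of Results treats it as a change score ("The amplitude of the score on the DTSQc gives the degree of change in satisfaction"), so it has no separate period 1 value.

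**What to change.** In Analysis of Secondary Endpoints, for continuous outcomes measured in both periods, replace the paired t-tests with a two-sample t-test between sequences on each patient's period 2 minus period 1 difference, and define the device effect as half the between-sequence difference. Alternatively, prespecify the linear mixed model with fixed treatment, period and sequence and a random patient effect. The two agree for complete data, and the model can also use patients with only one period. For the DTSQc, compare the single change score between sequences.

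The cost is wording and one degree of freedom, with no extra patients or data. Power for 0.41 SD stays at 80.4% with balanced completers, so the figure in Power Considerations need not change; aligning its test name is optional. Like the current plan, the fix assumes no differential carry-over. It also does not settle the non-inferiority or similarity margins, which are a separate matter.
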